## Specific aims

- What effect does written dietary advice have on LDL cholesterol (primary outcome) and other lipoproteins and risk factors (secondary outcomes) after 3 weeks and 6 months, compared with a control group?
- What proportion of individuals achieve a  $\geq 10\%$  reduction in LDL cholesterol from baseline, after 3 weeks and 6 months?
- In the group of responders ( $\geq 10\%$  reduction in LDL cholesterol from baseline), what is the effect after 3 weeks and 6 months?
- Is double sampling of LDL cholesterol required in clinical practice, i.e., how many would be misclassified as responders/non-responders if only one sample was taken at 3 weeks and 6 months?
- How does the intervention's cost compare with estimated future health care savings, as estimated per mean LDL cholesterol reduction, and per individual reaching  $\geq 10\%$  reduction in LDL cholesterol at 6 months?
- Which food choices are associated with reductions in LDL cholesterol in practice?
- What are the reasons given for wanting to reduce LDL cholesterol? Is there any association between reasons given and effect on LDL cholesterol?

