After day 21, participants will receive a standardized written letter containing results from the lab tests and personalized feedback depending on whether their LDL cholesterol has not improved ( $\leq 0\%$ ), improved little (0.1-9.9%), or clearly improved ( $\geq 10\%$  reduction). The control group will receive a letter similar to intervention group, but with effects on triglycerides replacing LDL cholesterol. The effects on triglycerides in control vs intervention groups will also be analyzed as a secondary outcome. However, LDL cholesterol is the surrogate marker most clinically useful and is considered causally related to atherosclerosis development. After day 183, all participants will receive another letter containing results from blood samples and the other groups' dietary advice. Further blood or other analyses will however not be offered as part of the study. In order to compensate for increased expenses, extra health care visits and to minimize loss to follow-up, all participants will receive 500 SEK (~50 €) after the final blood samples are drawn, independently of result on blood lipids or how many dietary changes have been made. Participants that are lost to follow-up at 6 months will however not receive this compensation. The participants will not receive any food items or any other lifestyle advice, in order to make the study environment as similar to clinical practice as possible.

Blood samples will be analyzed at Falu Lasarett using standard routines, during the same day or be kept cool and analyzed the following day, if the sample is drawn in the afternoon. LDL cholesterol is measured in plasma using direct method (P- LDL-Kolesterol SWE05408).

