### **Statistical analyses**

Based on previous randomized intervention studies of dietary fat quality and effects on lipoproteins, at least n=222 participants are required (for alpha = 0.05 and beta = 0.10) to detect an effect in LDL cholesterol of 0.175 mmol/L (~5%), which is an effect slightly exceeding that in most previous studies, parallels within-individual day-to-day variation (at double sampling), and has some clinical significance. This calculation takes into account a 20% loss to follow-up in the intervention group and a contamination effect of 5% in the control group.

The results will be analyzed according to intention-to-treat principle. Missing data at follow-up will be handled by imputing the baseline value. For LDL cholesterol, the mean value of the double analyses at days -3/0, 18/21 and 180/183 will be used. The CV of the biological variation will thus be decreased from 7 to 5%. Between-group comparisons for effects on all outcomes will be performed as a generalized linear model (GLM) in SPSS software, adjusted for factors *a priori* considered likely to modify effects (baseline values, BMI, age and sex). As sensitivity analyses, also unadjusted, non-parametric testing (Mann-Whitney U-test) will be performed. P<0.05 will be considered as statistically significant.

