Secondary outcomes: Change in HDL cholesterol, total cholesterol, fasting triglycerides, apo B, apo AI, apo B:AI, fasting glucose, HbA1c, systolic and diastolic blood pressure, weight, BMI and waist circumference at 6 months and 3 weeks. No. and proportion of individuals that achieve a $\leq 0\%$, > 0 to < 10% or $\geq 10\%$ reduction in LDL cholesterol from baseline, after 6 months and 3 weeks. Change in LDL cholesterol at 6 months and 3 weeks, in responders at 3 weeks (≥10% reduction in LDL cholesterol from baseline). No. and proportion of individuals misclassified at 6 months and 3 weeks with only sample 2, 4 and 6 included in analyses. Estimated cost of intervention. Associations of food choices (total no. and no. and proportion of total X:s for each dietary advice in food record table) with change in LDL cholesterol, and with HDL cholesterol, total cholesterol, fasting triglycerides, apo B, apo AI, apo B:AI, fasting glucose, HbA1c, systolic and diastolic blood pressure, weight, BMI and waist circumference at 6 months and 3 weeks. Reasons stated for wanting to improve blood lipoproteins, and associations with total no. and percentage of total of X:s in food record table and with changes in LDL cholesterol, HDL cholesterol, total cholesterol, fasting triglycerides, apo B, apo AI, apo B:AI, fasting glucose, HbA1c, systolic and diastolic blood pressure, weight, BMI and waist circumference at 6 months and 3 weeks. No. of individuals that develop impaired fasting

glucose, and elevated ALT at 6 months and 3 weeks. Change and average variation (CV) in LDL Cholesterol at 21 vs. 18 days and at 183 vs. 180 days.

Possible future analyses: Change in plasma Lipoprotein(a), serum PSCK9 and genes involved in lipid metabolism at 6 months and 3 weeks.

26b. Specific measurements and units

LDL cholesterol (direct method), HDL cholesterol, total cholesterol, fasting triglycerides and glucose in mmol/L.

Apo B and apo AI in g/L.

HbA1c in mmol/mol.

ALT in µkat/L.

TSH in mU/L.

Weight (in light clothing) in kg.

Height and waist circumference in cm.

BMI as kg/m^2 .

Systolic and diastolic blood pressure in mm hg.

Age at randomization in X.X years

Type 2 diabetes is defined according to current diagnostic criteria.

Impaired fasting glucose is defined as fasting P-glucose 6.1 - 6.9 mmol/L.

26c. Specific calculations

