For LDL Cholesterol baseline (BL) values will be calculated as the arithmetic mean of values at day -3 and day 0 [(d-3+d0)/2], similarly, values at 3 weeks will be calculated as the arithmetic mean of values at days 18 and 21 [(d18+d21)/2] and values at 6 months will be calculated as the arithmetic mean of values at days 180 and 183 [(d180+d183)/2].

For all continuous variables, absolute change from baseline (Δ) will be calculated at 3 weeks and 6 months as [Δ = 3w - BL and 6m - BL]. Relative change from baseline (% Δ) will be calculated as [% Δ = (3w - BL)/BL and (6m - BL)/BL].

As a sensitivity analysis, variables in the GLM with non-normal distribution will be log transformed (otherwise, no transformations will be performed).

Analysis methods

27a. Analysis methods and presentation of results

Between-group differences for change from baseline (Δ) in continuous variables will be significance tested using a general linear model (GLM). For LDL cholesterol, the results will be presented as a figure with boxplots displaying values at BL, 3 weeks and 6 months for each group. Also, a boxplot of Δ -values at 6 months will be presented for each group. The results will be given in a table format, displayed as mean±SD change from baseline, and P-values for difference between groups.

Difference in mean change from baseline in LDL cholesterol (and triglycerides for control group) between 21 and 18 days and 183 vs. 180 days will be analyzed with t-tests.

Secondary outcome no. 4 (success rate) i.e. the no. and proportion of individuals that achieve a $\leq 0\%$, >0 to <10% or $\geq 10\%$ reduction in LDL cholesterol from baseline will be analyzed by logistic regression, adjusted for age, sex and baseline BMI. No. of individuals that develop impaired fasting glucose will be compared between groups with Fisher's exact test (unadjusted).

Secondary outcome no. 8 (effective food choices) will be analyzed and presented as linear regressions between number of X:s for food choices 1-13 (and the total number of X:s) and change in LDL cholesterol (or Triglycerides within Control group) at 3 weeks and 6 months.

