Secondary outcome no. 9 (stated reasons) will be categorized into main groups of reasons according to given responses (one, two or three compared to none stated), no. in each group and mean changes in LDL cholesterol (or triglycerides) as well as total number of X:s (and proportions of total number of possible X:s for both groups combined) will be given as means+SD in table format. For within-group effects on mean LDL cholesterol at 3 weeks and 6 months, paired t-tests will be performed in intervention group (the same for triglycerides in control group). For proportion of total X:s, differences compared with reference group (none stated) will be analyzed by Mann Whitney U-test.

27b. Adjustment for covariates

Comparisons of means in the GLM will be adjusted for the baseline value of the variable, baseline BMI, age and sex.

For success rate, the logistic regression will be adjusted for the covariates baseline LDL cholesterol, baseline BMI, age and sex.

Linear regressions for food choices and lipoproteins will be unadjusted.

27c. Tests for assumptions

Normality of data will be determined by visual inspection of histograms and QQ-plots. No other tests for assumptions will performed. The underlying assumptions of the GLM will be tested by examining residuals.

27d. Alternative methods if distributional assumptions do not hold

As a sensitivity analysis, variables in the GLM with non-normal distribution will be log transformed (otherwise, no transformations will be performed).

27e. Planned sensitivity analyses

For all comparisons of means of continuous outcomes, unadjusted Mann Whitney U-tests will be performed as sensitivity analyses.

27f. Planned subgroup analyses

In order to investigate whether different baseline characteristics are associated with success rate (outcome no. 4), responders (≥10% decrease in LDL cholesterol or Triglycerides) and non-responders at 3 weeks will be analyzed with descriptive statistics regarding age, sex, baseline cholesterol, no. with diabetes and impaired fasting glucose, systolic and diastolic blood pressure, no. of X:s (total and for each food choice), and reasons stated (according to categories), separately for both study arms. Comparisons between responders and non-responders will be analyzed by t-tests and Fisher's exact test. Similar analyses will be performed for successful individuals at 6 months (≥10% decrease in LDL cholesterol or Triglycerides).

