Further, subgroup analyses will be performed in young (<65 years) vs elderly (65+) individuals, in order to establish whether results are homogenous in these subgroups, for guidance of future studies.

28. Missing data

When data are missing due to loss to follow-up, baseline values will be imputed. If only one time point 3 or 5 is missing (LDL cholesterol at d18 or d180), the mean LDL

cholesterol value will instead be assumed to be the exact value at time point 4 or 6 (d21 or d183).

29. Additional analyses

For possible future analyses (see 26a. secondary outcomes), analyses will be performed with similar methods as other continuous/categorical variables.

30. Harms

Reported adverse effects (if any) will be described in text or table format, depending on the outcome. No serious adverse effects are expected and severity will not be summarized separately.

31. Statistical software

IBM SPSS Statistics 25 will be used for all analyses.

32. References

Data management plan, standard operating procedures, dietary advice, food records and study letters will be stored separately and not provided at trial registry during the study. No statistical master file has yet been created and public access will not be granted.

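### The LDL change reported in 3-week responders is partly created by how they are selected: with no true change they would still show falls of about 0.47 mmol/L at 3 weeks and 0.22 at 6 months

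*SAP*

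**What the plan says.** The Protocol (Specific aims) asks, for participants with a fall of at least 10%: "reduction in LDL cholesterol from baseline), what is the effect after 3 weeks and 6 months". The SAP repeats this aim under Objectives. Item 26a turns it into an outcome: "Change in LDL cholesterol at 6 months and 3 weeks, in responders at 3 weeks (≥10% reduction in LDL cholesterol from baseline").

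Item 26c defines the measurements: "For LDL Cholesterol baseline (BL) values will be calculated as the arithmetic mean of values at day -3 and day 0". The 3-week value is the mean of days 18 and 21, the 6-month value is the mean of days 180 and 183, and both changes are taken from that one baseline.

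Item 27f adds that "responders (≥10% decrease in LDL cholesterol or Triglycerides) and non-responders at 3 weeks will be analyzed with descriptive statistics", separately in each arm. Item 28 says: "When data are missing due to loss to follow-up, baseline values will be imputed". The 10% threshold also decides which feedback letter is sent after day 21; the Protocol (Methods) grades the LDL result as not improved, "improved little (0.1-9.9%), or clearly improved".

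Item 26a does not say in which arm the responder change will be reported. The SAP sets out no correction, caveat or comparator for it.

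**The concern.** A responder is someone whose observed 3-week mean is at least 10% below the observed baseline mean. Two problems follow.

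- **3 weeks.** The change is computed from the same two means that did the selecting, so it is at least a 10% fall by construction.
- **6 months.** The follow-up samples are new, but the baseline is the one used for selection. In selected people it is too high on average, so a fall appears even if nothing has changed.

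The 6-month figure is the more misleading of the two. It could be read as a lasting response in the people who were told they had clearly improved, when part or all of it is regression to the mean. One stated aim would then be answered with a number that does not measure what the aim asks.

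**Working it through.** **Inputs**

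- Within-person CV, Protocol (Statistical analyses): "The CV of the biological variation will thus be decreased from 7" to 5% by double sampling. Check: 7%/√2 = 4.95%, so the stated 5% is reproduced.
- Mean LDL is not stated. The power calculation is "to detect an effect in LDL cholesterol of 0.175 mmol/L (~5"%), which implies 0.175/0.05 = 3.5 mmol/L. A range of 3.0 to 4.0 is shown below.
- Participants: 113 at 1:1 (SAP item 11), so 56 or 57 per arm.
- Loss to follow-up: 20% in the intervention group, from the power calculation.
- Assumed: normal errors, independent between samples, the same CV at every visit.

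**No true change, closed form**

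Let T = 3.5 be the true LDL, B = T + e0 the baseline mean and W = T + e1 the 3-week mean. Each error has SD 3.5 × 0.07/√2 = 0.173.

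1. Responder: W ≤ 0.9B, that is U = e1 − 0.9e0 ≤ −0.35.
2. SD(U) = 0.173 × √(1 + 0.81) = 0.233, so the cut-off lies 0.35/0.233 = 1.50 SD below the mean.
3. P(responder) = 1 − Φ(1.50) = 0.067. Per arm: 57 × 0.067 = 3.8, about 4 people.
4. Mean of U in responders = −0.233 × φ(1.50)/0.0666 = −0.233 × 1.94 = −0.452.
5. This splits into e1 = −0.452/1.81 = −0.250 and e0 = +0.9 × 0.452/1.81 = +0.225.
6. Change at 3 weeks = −0.250 − 0.225 = **−0.475**. Change at 6 months = 0 − 0.225 = **−0.225** mmol/L.

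A simulation of 2,000,000 people agrees: 6.65% responders, −0.475 and −0.225 mmol/L, or 12.7% and 5.9% of observed baseline. With the double-sample CV set to exactly 5%, the results are 6.9%, −0.477 and −0.226.

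**Other assumptions, still no true change**

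| Assumption | Fall at 3 weeks | Fall at 6 months |
|---|---|---|
| Mean LDL 3.0 | 0.41 | 0.19 |
| Mean LDL 3.5 | 0.47 | 0.22 |
| Mean LDL 4.0 | 0.54 | 0.26 |
| LDL 3.5, 10% of responders lost, baseline imputed | 0.47 | 0.20 |
| LDL 3.5, 20% of responders lost, baseline imputed | 0.47 | 0.18 |

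Letting true LDL vary between people (SD 0.7 to 0.9) leaves the LDL 3.5 result at 0.47–0.48 and 0.22–0.23 if error is proportional to LDL. If the error SD is constant, the falls are 0.43–0.44 and 0.20–0.21.

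**A true 3-week change averaging −5% that is gone by 6 months**

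| SD of true change (assumed) | Shown, 3 weeks | True, 3 weeks | Shown, 6 months | True, 6 months |
|---|---|---|---|---|
| 0% | 0.496 | 0.175 | 0.161 | 0 |
| 3% | 0.510 | 0.231 | 0.141 | 0 |
| 5% | 0.533 | 0.305 | 0.116 | 0 |
| 7% | 0.566 | 0.382 | 0.095 | 0 |

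With 20% loss and baseline imputation the 6-month falls become 0.128, 0.113, 0.093 and 0.075. A response that has vanished would still look partly maintained.

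**The case against.** The strongest reply has four parts.

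- **The null case is only one scenario.** This is fair. If a −5% change persists, responders show about 0.33 at 6 months against a true 0.175 (no variation in true change), or about 0.47 against 0.38 (SD 7%). Much of the figure is then real. The excess is still about 0.15 down to 0.09, as when the effect vanishes. So 0.47 and 0.22 describe what noise alone can produce and must not be subtracted from an observed result.
- **The SAP already reports noise.** Item 26a plans the number misclassified when single samples are used, and the LDL variation between days 18 and 21 and between days 180 and 183. These are useful, but they neither correct the responder change nor give a reference value for it. Double sampling is already built into the 5% CV. Item 27f compares responders with non-responders within each arm, which leaves the selection in place, and its wording (LDL or triglycerides) does not guarantee an LDL-defined group among controls.
- **The outcome is descriptive.** Item 26a speaks of change, no test is named for this outcome, and item 16 calls secondary outcomes mainly hypothesis generating. This limits the harm. The aims nevertheless ask for an effect, and following early responders to 6 months is a legitimate question that deserves a readable answer.
- **20% loss after week 3 is a high assumption.** This is correct. A participant already lost by week 3 has baseline imputed and cannot be a responder. The 6-month null figure therefore probably lies between 0.18 and 0.22. Comparison with the 0.175 target conveys scale only, because that target is a between-arm difference.

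**Conclusion.** The concern holds. Under the plan as written, noise alone would give 3-week responders a mean LDL fall of about 0.47 mmol/L at 3 weeks and 0.22 at 6 months. With a real average change of −5%, the 6-month figure would still be too large by roughly 0.09 to 0.16.

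These sizes rest on the protocol's CVs, the implied mean LDL of 3.5 and errors independent between visits. Assay error beyond the stated CV would raise them; positive correlation of errors between visits would lower them. The direction of the bias does not depend on the exact values.

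The damage is confined to this one secondary aim. The primary between-arm comparison and the comparison of responder proportions are not affected.

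**What to change.** Keep the planned responder group and make four changes in the SAP:

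1. State that the change in responders is descriptive and affected by selection, and is not an estimate of the effect of the advice.
2. Report the same summary, with n and spread, for LDL-defined responders in the control arm. Present it as a noise reference, not as a randomized comparison.
3. Rest the conclusion on the logistic regression of responder status already planned in item 27a and on the comparison of all randomized participants.
4. Add a split-sample sensitivity analysis. Classify on days −3 and 18, then estimate the change from day 0 to day 21 and from day 0 to the day 180/183 mean. Leave out participants with filled-in samples.

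The cost is SAP wording and a small re-analysis of data already collected. The limits should be stated alongside:

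- With no true change, only about 4 control participants would be responders (5th to 95th percentile 1 to 7), so the noise reference is imprecise.
- Single-sample classification is noisier. With no true change it selects 14.4% of people instead of 6.7% and includes 66% of the planned responders, so the group differs from those sent the most favourable letter.
- The split removes the bias fully only if errors three days apart are independent. With a within-pair correlation of 0.3, spurious falls of 0.16 and 0.08 mmol/L remain at 3 weeks and 6 months. With 0.5, they are 0.27 and 0.13, against 0.51 and 0.24 for the planned summary under that same correlation.

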Statistical analysis plan (SAP)

Section 1. Administrative information

1a. Title, registration, versions and revisions

Full study title: Effectiveness of Written Dietary Advice on Lipoproteins - a Pragmatic Randomized Controlled Trial

Acronym: MYDICLIN

1b. Clinicaltrials.gov identifier: NCT03528252

2. SAP version: 1.4, 2019-04-18

3. Protocol version: Research plan version 18-09-20

4. SAP revisions: No major revisions.

5. Roles and responsibility

Author: [name]^{1,2}

Principle Investigator: [name]^{1,2}

Affiliations:

- 1. Unit for Clinical Nutrition and Metabolism, Deptartment of Public Health and Caring Sciences, Uppsala university.
- 2. Center for Clinical research Dalarna

6. Signatures:

I the undersigned, certify that I have read this SAP and approve it as adequate in scope of the main analyses of MYDICLIN.

6. Author and principle investigator

Name: [name]

Date: 2019 - 04 - 18

Section 2. Introduction

7. Background and rationale

Dietary factors are of major importance for public health, but effective means are lacking, to improve dietary habits of patients in primary care. This pragmatic trial aims to investigate whether detailed written dietary advice may be an effective way of improving blood lipoproteins in a Swedish primary care setting.

8. Objectives

The main purpose is to investigate whether written dietary advice with individual written feedback can affect blood lipoproteins in the short-term (3 weeks) and medium-term (6 months).

Specific aims

- What effect does written dietary advice have on LDL cholesterol (primary outcome) and other lipoproteins and risk factors (secondary outcomes) after 3 weeks and 6 months, compared with a control group?
- What proportion of individuals achieve a ≥10% reduction in LDL cholesterol from baseline, after and 6 months?
- In the group of responders (≥10% reduction in LDL cholesterol from baseline), what is the effect after 3 weeks and 6 months?
- Is double sampling of LDL cholesterol required in clinical practice, i.e., how many would be misclassified as responders/non-responders if only one sample was taken at 3 weeks and 6 months?
- How does the intervention's cost compare with estimated future health care savings, as estimated per mean LDL cholesterol reduction, and per individual reaching ≥10% reduction in LDL cholesterol at 6 months?
- Which food choices are associated with reductions in LDL cholesterol in practice?

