P<0.05 will be considered as statistically significant for primary outcomes. For secondary outcomes, significance testing is not as essential as they are mainly hypothesis generating.

17. Adjustment for multiple analyses

The primary outcome is change in LDL cholesterol at 3 weeks and 6 months. The power calculations have been performed for between-group differences at 6 months and this analysis is considered the primary outcome of the study. Thus, no adjustment for multiple analyses will be performed.

18. Confidence intervals

N/A.

Adherence and protocol deviations

19a. Definition of adherence to the intervention

Being randomized and completing the trial (day 183) is considered as sufficient for adherence. For the visit at 3 weeks, no more than 2 days' deviation from protocol will be allowed. For the visit at 183 days, no more than 2 weeks' deviation will be allowed.

19b. Description how adherence will be presented

No specific information on adherence will be presented, besides no. of participants randomized and completing the trial at 3 weeks and 6 months, and no. excluded before and after randomization, with reasons.

19c. Definition of protocol deviations

Deviations from time schedule. Failing to be overnight fasting at time points 2, 4 or 6.

19d. Description of which deviations will be summarized

In cases in which blood samples are taken on the wrong day, the no. of deviations and number of days' deviation from protocol will be reported for each time point. Also, the number indivduals who failed to be completely fasting at time points 2, 4 and 6 will be given.

20. Analysis populations

Study populations will be analyzed according to intention-to-treat principles.

Section 5. Trial Population

21. Screening data

N/A (not collected).

22. Eligibility criteria

Inclusion criteria: patients listed at the health care centre, wish to improve blood lipoproteins, ages 18-99 years.

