Exclusion criteria: drugs affecting lipid metabolism (statins, ezetemibe, fibrates, PCSK9 inhibitors, neuroleptics, cortisone, amiodarone, estrogen, progesterone, testosterone, cyclosporin, tacrolimus, loop diuretics, protease inhibitors and anti-convulsants, whereas beta-blockers, tiazid-diuretics and SGLT2 inhibitors are accepted at stable use), malignant disease, extreme diet (vegan diet, strict low-carbohydrate diet, other weight-loss diet), disturbed metabolism e.g. untreated hypothyroidism or hyperthyroidism, dementia or inability to understand written Swedish instructions, other participant from same household, current employment at the health care centre.

23. Recruitment

Information on no. enrolled (assessed for eligibility, excluded – with reasons and randomized), allocated, lost to follow-up or discontinued (with reasons) and analyzed or excluded from analysis (with reasons) will be presented in a CONSORT flow diagram.

Withdrawal/follow-up

24a. Level of withdrawal

No. of participants withdrawn or lost to follow-up will be presented for each group.

24b. Timing of withdrawal/lost to follow-up data

Timing of withdrawal or loss to follow-up will be presented for each group.

24c. Reasons and details of withdrawal/lost to follow-up data

Reasons and details will be presented in a CONSORT flow diagram and in text format (Results).

Baseline characteristics

25a. List of baselines characteristics

Age, sex (male/female), diabetes (yes/no), impaired fasting glucose (yes/no), body weight, BMI, waist circumference, systolic and diastolic blood pressure, LDL cholesterol, total cholesterol, HDL cholesterol, fasting triglycerides, apo B, apo AI, apo B:AI, fasting glucose and HbA1c will be presented for each group in table format (without significance testing of variable distributions).

25b. Details of baseline characteristics presentation

Non-normal variables will be presented as median, IQR, otherwise as mean +SD or n for categorical variables.

Section 6. Analysis

Outcome definitions

26a. Primary outcome: Change in LDL cholesterol at 6 months (primary analysis) and 3 weeks.

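### The SAP does not plan to report the adjusted 6-month LDL difference, its primary quantity, as an estimate with a confidence interval

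*SAP*

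**What the plan says.** - **SAP item 27a** tests change from baseline in continuous variables between groups with a GLM. The table is "displayed as mean±SD change from baseline, and P-values for difference between groups". The LDL figures are per-group boxplots of values at the three time points and of the 6-month change.
- **SAP item 27b** makes that P-value covariate-adjusted: "Comparisons of means in the GLM will be adjusted for the baseline value of the variable, baseline BMI, age and sex".
- **SAP item "18. Confidence intervals"** has N/A as its whole entry.
- **SAP item 17** identifies the primary quantity: "The power calculations have been performed for between-group differences at 6 months and this analysis is considered the primary outcome of the study". Item 26a agrees.
- **SAP item 16** plays down testing for the rest: "For secondary outcomes, significance testing is not as essential as they are mainly hypothesis generating".
- **SAP item 23** commits to numbers "analyzed or excluded from analysis (with reasons) will be presented in a CONSORT flow diagram".
- **SAP item 27e** adds that "unadjusted Mann Whitney U-tests will be performed as sensitivity analyses".
- **Protocol, Statistical analyses** names the adjusted GLM and the 0.05 threshold, but no effect estimate or interval.

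**The concern.** The first specific aim asks how large an effect the written advice has on LDL cholesterol compared with control. A P-value does not answer that. Under the plan as written, the adjusted difference would enter the results only through its P-value, beside per-arm summaries that are not described as adjusted.

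This matters more because recruitment closed at 113 against an initial requirement of 222 (SAP item 11). If the primary P-value is above 0.05, only an interval shows whether 0.175 mmol/L, or the 0.07-0.16 mmol/L that the Protocol's Background cites from earlier studies, remains compatible with the data. If it is below 0.05, only an interval shows how small the effect could be.

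For the continuous secondary outcomes, item 16 gives significance testing less weight, yet a P-value is the only between-group quantity that item 27a tables for them.

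**Working it through.** **1. What a reader could recover from the planned output**

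| Quantity | Recoverable? | Source |
|---|---|---|
| Unadjusted difference in change | Yes | Per-arm means, item 27a |
| Unadjusted 95% CI | Yes | Per-arm SDs (27a) and numbers analysed (23) |
| Adjusted P-value | Yes | Items 27a and 27b |
| Adjusted difference and its 95% CI | No | Not planned in any section |

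The Mann-Whitney test in item 27e is unadjusted and rank-based, so it does not supply the last row. This comparison carries the point; the rest only gives a sense of size.

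**2. An SD for illustration**

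The documents state no SD, so the stated sample sizes cannot be reproduced from stated inputs. Working backwards (two-sided alpha 0.05 assumed, 1:1), total N = 4(z₁₋α/₂ + z₁₋β)² SD²/δ². With SD = 0.30 mmol/L, rounding each arm up:

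- 90% power, δ = 0.175 × 0.75 = 0.131 (20% loss and 5% contamination both treated as dilution): N = 220; stated 222.
- 80% power, δ = 0.175 × 0.95 = 0.166 (contamination only): N = 104; stated 106.
- 80% power, δ = 0.175: N = 94; stated 94.

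A t-based calculation gives 222, 106 and 96. The fit is close, but it needs the 20% loss to count for 222 and not for 106, which item 11 does not say. With other ways of entering the allowances, 222 implies an SD of up to about 0.40. The value 0.30 is therefore an assumption.

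**3. Width of the unadjusted interval at n=113 (56 vs 57)**

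SE = 0.30 × √(1/56 + 1/57) = 0.0564. Half-width = 1.96 × 0.0564 = 0.111 mmol/L, and 0.111/0.175 = 63% of the target effect. The half-width scales as 0.369 × SD: 0.092 at SD 0.25, 0.129 at 0.35 and 0.148 at 0.40.

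**4. Adjusted against unadjusted**

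This adjusts for baseline LDL only, with equal baseline and follow-up variances and an assumed correlation r. BMI, age, sex and the baseline imputation of item 28 are not modelled.

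- SE ratio (adjusted/unadjusted) = √((1+r)/2).
- SD of the gap between the two estimates ≈ √((1−r)/2) × 0.0564.
- LDL SD implied by r = 0.30/√(2(1−r)).

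| r | Implied LDL SD | SE ratio | Adjusted half-width | Typical gap (1 SD) |
|---|---|---|---|---|
| 0.80 | 0.47 | 0.949 | 0.105 | 0.018 |
| 0.92 | 0.75 | 0.980 | 0.108 | 0.011 |
| 0.50 (extreme) | 0.30 | 0.866 | 0.096 | 0.028 |

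The gap formula is a large-sample one. Simulated gaps are slightly larger, about 0.019 at r = 0.80.

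**5. How often the adjusted P-value and the rebuilt interval fall on different sides of 0.05**

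Simulation of 20,000 trials per cell, pooled t-test on change against ANCOVA on baseline:

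| True effect (mmol/L) | r = 0.80 | r = 0.92 | r = 0.50 (extreme) |
|---|---|---|---|
| 0 | 3.0% | 1.8% | 4.6% |
| 0.07 | 8.0% | 5.0% | 14.8% |
| 0.11 | 11.0% | 6.6% | 18.4% |
| 0.175 | 5.7% | 3.7% | 8.6% |

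A repeat run agreed to within about 1 percentage point in every cell.

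**6. Why r = 0.50 is an extreme case**

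The plan equates 0.175 mmol/L with about 5%, so mean LDL is about 0.175/0.05 = 3.5 mmol/L. An LDL SD of 0.30 would put about 95% of participants between 2.9 and 4.1 mmol/L. The trial admits ages 18-99 with no LDL limit at entry, so such a narrow spread is hard to credit.

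**The case against.** The strongest case against the point is that little is lost. In a randomised trial with a linear model, the adjusted and unadjusted differences estimate the same treatment effect. They differ through chance covariate imbalance, and the unadjusted one is slightly less precise. The tabled arm means therefore give an unbiased estimate of the effect that the P-value tests, and the boxplots show direction and spread. That stands. A reader might infer that the printed P-value would correspond to no reported effect at all, but the documents do not support so strong a reading.

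A reader might also take the largest figures, an interval 13% narrower and disagreement in up to 18% of trials, as the expected size. They need r = 0.50 and the implausibly narrow LDL spread that goes with it. Imputing baseline values for dropouts (item 28) would raise the correlation further and shrink the differences; adding BMI, age and sex would widen them somewhat. Disagreement is also greatest at a true effect of 0.11 because unadjusted power there is about 49%, where any two correlated tests part most often.

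The tabled means might be meant as adjusted means, and nothing forbids the authors from reporting intervals. But the SAP does not call the means adjusted, an SD of change is naturally a per-arm descriptive figure, and N/A under a dedicated heading is an explicit entry. Extending adjusted intervals to every continuous secondary outcome is closer to preference than to need.

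**Conclusion.** The point holds as a reporting gap. Item 27a specifies the presentation and item 18 declines intervals, so following the SAP would leave the primary 6-month comparison without its adjusted estimate or any interval. This conclusion rests on the text alone.

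The size is illustrative and rests on an assumed SD of change of 0.30 mmol/L, n=113 and a correlation of 0.8 to 0.92. The missing interval matters chiefly because it is wide: about ±0.11 mmol/L against a target of 0.175. What the rebuilt unadjusted version gets differently is modest. Its interval is wide enough that the adjusted one would be 2-5% narrower, and the estimates typically differ by 0.011-0.019 mmol/L. The verdict at 0.05 differs in about 2-3% of trials at no effect, 5-8% at 0.07, 7-11% at 0.11 and 3-6% at 0.175.

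A reader might infer that the primary analysis is biased or its error rate inflated. Nothing here supports that: the model, the test and the alpha level are unaffected.

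**What to change.** - **Item 18:** replace N/A with two-sided 95% confidence intervals.
- **Item 27a:** report the GLM-adjusted between-group difference in LDL change, with its 95% CI and P-value, at 6 months (primary) and 3 weeks. Keep the per-arm mean±SD change and label it as unadjusted.
- **Optional:** do the same for the continuous secondary outcomes, labelled as descriptive in line with item 16.

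The cost is one more table column. The planned GLM already yields the difference and its interval, so no new data, model or test is needed.
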